#### 7.1.3. Participant Screening

Identified potential participants who are eligible for an NHS Health Check and QRISK®2 evaluation will be considered for participation in the study, unless the investigator considers the potential participant unsuitable for the study.

The study invitation letter will be provided with a copy of the patient information sheet (PIS) and consent form (on surgery headed paper). Study sites participating in the saliva sub-study will provide the PIS and consent form for the saliva sample as well.

A screening log of those identified by search will be maintained, documenting when invites are sent, if they are not invited or if they fail to respond. For ease, this can be documented on a print out of the search results, or a separate screening log can be maintained. The screening log, in whichever format used, will be filed in the Investigator Site File (ISF).

#### **7.1.4. Participant Payment**

Participants may be reimbursed for reasonable travel expenses, but no other payments will be made.

#### **7.1.5. Participant Consent**

The Principal Investigator (PI) will retain overall responsibility for the conduct of research at their site, including the taking of written informed consent of participants at their site. They will ensure that any person delegated responsibility to participate in the informed consent process is duly authorised, trained and competent to participate according to the ethically approved protocol, principles of Good Clinical Practice (GCP) and Declaration of Helsinki.

Physicians or practice nurses will take consent, as per delegation log.

Written informed consent will be obtained from the participant after they have been given adequate time and opportunity to discuss any study related questions with the health care team. Consent is anticipated to be provided during an appointment (in person) with the health care team, but may also be provided remotely, via telephone or video conference, and written consent will be obtained before any other study procedures (data and biosample collection) commence.

The staff member recording consent will be responsible for assessing the capacity of the interested participant to provide informed consent.

Patients will be informed that if they decline to participate in the study (without having to give a reason), that decision will not compromise their ongoing health care.

The sponsor will keep anonymised genetic data to support future research. If the participant does not wish to allow the sponsor to keep genetic data for future research, they will not be able to participate in the study.

The participant will remain free to withdraw at any time from the study without having to give a reason and without prejudicing their further management and will be provided with a contact point where they may obtain further information about the study. Where a participant is required to re-consent or new information is required to be provided to a participant it is the responsibility of the PI to ensure this is done in a timely manner.

The original signed consent form will be provided to the participant, and copies filed in the investigator site file (ISF) and participant medical notes if required by local practice.

#### **7.1.6. Additional participant consent provisions for collection of saliva samples and interviews**

Around 100 participants (at 1-2 sites) of the 1000 participant population will be asked to provide saliva samples for a subanalysis of the study, looking at the capability of using DNA extracted from saliva samples for genetic analysis. A separate information sheet and consent form will be provided for the provision of saliva samples.

[figure not shown]
Participants asked to provide saliva samples can decline to do so and still participate in the main study.

Around 20-30 participants will be invited for an interview after one third of participants have been recruited. The participants will be selected by the qualitative researcher from data provided by the sponsor on participants who have provided consent to take part in the interview as described in

7.1.6.1. The researcher will notify the relevant site clinical study team to identify and pass on contact details to the qualitative researcher.

#### 7.1.7. Participant Study assessments, per visit

A participant's journey will include 3 visits, and potentially up to 4 visits, as demonstrated in Figure 2.

**Figure 3: Patient Participant Flow Diagram.** Only patient participant visits are outlined in the schedule above. The HCP questionnaires and focus groups (HCP and PCC) will be conducted in parallel with the participant Interviews where necessary.

##### 7.1.7.1. Visit 1, Baseline

Before (remotely) or During Visit 1, the participant will have the opportunity to further review the information sheet and have any questions answered before signing a consent form. The participant should only sign and date the consent form if they wish to participate in the study. If for any reason they are unwilling or unable to sign the consent form, they cannot participate in the study.

After approximately  $\frac{1}{3}$  of participants are enrolled, subsequent participants will be asked if they are willing to consent for selection to take part in an interview, consisting of a 30 minute telephone interview about the study, approximately 1-2 months after receiving their results. If the participant

agrees to take part they are asked to sign the interview consent form at Visit 1. Information to be collected at Visit 1 after written informed consent has been obtained will comprise:

- date of visit
- date of consent
- confirmation of eligibility
- date of blood sample
- age at time of sample
- biological sex
- self identified ethnicity
- educational level
- date of consent for saliva sample (if applicable)
- date of saliva sample (if applicable)
- QRISK®2 score (when available)
- questionnaire (4 questions to participants).

Since the study requires the participant to receive an online questionnaire, the site will require the participant's email address. This will be documented in the enrolment log.

Study eligibility will be confirmed by a member of the study team (as per delegation log) using participant medical notes and questioning the participant, and eligibility will be documented in the Case Report Form (CRF), but no details of the medical history will be collected for the purposes of the study.

When eligibility has been confirmed, the participant will be added to The HEART Application using their age and biological sex. The study staff will be trained on the use of The HEART Application and receive instruction for use (IFU), electronic Case Report Form (eCRF) and sample handling and posting and their site responsibilities. The system will generate a participant ID, which is used to identify the participant in all study documentation and added to the enrolment log, participant medical notes, sample shipping logs, adverse and serious adverse device event in the eCRF.

Since all participants are attending for a CVD risk assessment, they will be providing a blood sample as part of the process. The study requires blood to be taken using a butterfly and vacutainer holder, which will allow all blood samples (standard care and study) to be obtained via a single venepuncture.

The study samples will be prepared as described in the 'Sample Handling and Shipping Instructions Manual'. To ensure tracking, the samples will be labelled with a barcode and its human readable form (a six-digit number (XX-YYY-Z). The six-digit number is entered into The HEART Application. Spare labels are provided.

Before the participant leaves Visit 1, they will be asked to complete a short questionnaire (4 questions) on paper, with their participant ID and date of visit completed on the questionnaire. Participants hand the completed form to the study staff before they leave. Study staff enters questionnaire answers to the participants data in the eCRF.

When the QRISK®2 score is available, this will be added to The HEART Application as it is required to calculate the CVD IRT.

QRISK®2 score will be provided to the participant at the same time as the CVD IRT to simplify the process for the participant (unless physician intervention based on the QRISK 2 is needed before the

CVD IRT is available), so as not to receive two separate scores for the risk of developing CVD at different times.

In the event that a CVD IRT score cannot be provided to the participant, a replacement sample will not be sought and the participant's QRISK®2 score will be used to determine the standard of care. This may be due to loss of sample in transit to the laboratory or under the quality controls for sample processing, the sample integrity does not yield adequate DNA or the PRS score cannot be generated.

#### **7.1.7.2. Saliva Samples**

If the participant is attending a clinic recruiting for the saliva subanalysis, they will be asked to provide a saliva sample. They will be given the opportunity to review a separate information sheet and sign a separate consent form. They may decline the substudy while still participating in the main study. They will provide a 2ml sample, which will be labelled and packaged according to the instructions, and sent to a separate laboratory for DNA extraction.

There is a small possibility that saliva samples go missing in transit to the laboratory, despite processes in place to mitigate the risk. If this is the case, there will be no impact to the participant and they will not be asked to provide a replacement sample.

Saliva samples are for research purposes only. The CVD IRT will be based on blood samples not saliva samples.

#### **7.1.8. Visit 2, Receiving CVD IRT results and study participant management**

Approximately 5-12 weeks after the blood sample collection, the CVD IRT result will be available. The study staff will be notified of its availability by email and will be able to download the CVD IRT report from The HEART Application. Study personnel will be trained on the content of the report and best practice on sharing genetic information. Only those trained and listed on the delegation log will be permitted to share the CVD IRT results with the participants.

Current NICE guidance recommends intervention if the ten-year risk of CVD is greater than 10%. Both QRISK®2 and CVD IRT produce estimates of 10-year CVD risk, therefore, where the QRISK®2 and / or the IRT score exceeds 10%, NICE guidance is recommended to be followed.

The IRT report will be available up to 12 weeks after the sample is taken. If QRISK®2 indicates intervention is needed within this timeframe, the physician's discretion should be used.

The HCP will determine the best method of sharing the results (QRISK®2 and CVD IRT) as per standard practice. Participants may be contacted by phone or videoconference or may be asked to attend the clinic in person.

At Visit 2 the following data will be collected:

- date of visit
- the method of sharing results, e.g., phone, videoconference or clinic visit
- who shared results, e.g., GP or nurse
- whether QRISK®2 score required change in treatment (e.g., statin, life style, both or none influenced the change)
- any change in treatment (e.g. statin)

- if the participant's CVD IRT score was higher than their QRISK score, whether the CVD IRT score influenced (or informed on) a change in treatment (e.g. statin, lifestyle, both or none)
- what treatment was changed
- the participant will be asked about any potential adverse events since the previous visit.

The report is intended for HCP use to share results, but if requested by the participant a copy can be provided. The participant should be reminded of the online questionnaire and its importance to the study which will be sent to their email address in around 0-14 days' time. The study staff should also ensure that the participant's personal email address is available and correct on the enrolment log, for the above purposes and for participation in Interviews, if required by NECS.

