#### **7.2.3. Schedule**

There will be two questionnaires for HCPs to complete -

- 1) At Visit 2 - When the CVD IRT report has been received and discussion with the participant has taken place, the HCP will be required to complete a focused questionnaire in the eDC.
- 2) When at least  $\frac{1}{3}$  of the site's participants or at least  $\frac{1}{3}$  of the total study participants (whichever is first for each site) have completed Visit 2, the clinical study team will be provided with a link to an online questionnaire, designed specifically for the physicians and nurses who have participated in the clinical study. The questionnaire will take approximately 20 minutes to complete.

The HCPs will be reminded to complete the questionnaire a maximum of two times.

When no more questionnaire responses are anticipated, focus groups will be arranged selecting HCPs from those that have completed the questionnaire.

The timeline of the focus groups will be towards the end of participant participation at site, and the completion of the HCP questionnaires. It is intended that focus groups may be conducted in parallel with the participant interviews. It is anticipated that the interviews will be conducted as close to or just after all participants have completed Visit 2.

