#### **10.3.1. Operational analysis**

Analysis of the primary objective includes a calculation of the return rate of reports. In addition, an in depth analysis of the operational process of returning reports to the surgery will be undertaken.

A comparative analysis will be undertaken to explore incidences of reclassification between a patient's QRISK®2 score and their combined risk score.

The analysis will explore and assess the impact of the CVD IRT on clinical decision making where the addition of genetic information shows an increase in risk.

A comparative analysis will be undertaken of PRS derived from DNA extracted from blood and saliva.

Further analysis may be undertaken, guided by the interpretation and understanding of study results.

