| Secondary Objectives | | | |
| To explore and assess the impact of the CVD IRT on clinical decision-making | HCP feedback via questionnaires and focus groups | 
"TFLs_TOC_HEART_Example_layouts/DT2 2ry-1" (V2eDC-Q4, V2eDC-Q3, V2eDC-Q5, HCPQ-Q6, HCPQ-Q7, HCPQ-Q9, HCPQ-Q19, HCPQ-Q20)
 
"TFLs_TOC_HEART_Example_layouts/T10 HCPQual" (Comments relevant to objective compiled from free text responses to V2eDC-Q4, HCPQ-Q8, HCPQ-Q10, HCPQ-Q12, HCPQ-Q15 and HCPQ-Q24, and from HCP focus group discussions)
 | 
"TFLs_TOC_HEART_Example_layouts/T4 V2eDC-1" (HCP views summed over all participants processed)
 
"TFLs_TOC_HEART_Example_layouts/T5 V2eDC-2" (HCP views at start of study)
 
"TFLs_TOC_HEART_Example_layouts/T6 V2eDC-3" (HCP views at end of study)
 
"TFLs_TOC_HEART_Example_layouts/T8 HCPQ"
 |
| To assess the magnitude of the change in risk score between QRISK®2 and CVD IRT | QRISK®2 and CVD IRT scores to be compared | "TFLs_TOC_HEART_Example_layouts/DT3 2ry-2" | 
"TFLs_TOC_HEART_Example_layouts/T12 Risks"
 
"TFLs_TOC_HEART_Example_layouts/T13 Risk classification"
 
"TFLs_TOC_HEART_Example_layouts/T14 Deltas freq"
 
Ordered plot of deltas (CVD IRT minus QRISK®2) across individuals.
 |

| | | | |
|--|--|---|---|
| | | | Histograms of CVD IRT and QRISK®2 distributions, overall and split by age group, by sex, by ethnicity and by education level. |
| To explore and assess to what extent HCPs and PCCs perceive the CVD IRT as operationally efficient and enhancing the service that they provide | HCP feedback via questionnaires and focus groups | 
“TFLs_TOC_HEART_Example_lay outs/DT4 2ry-3” (V2eDC-Q6, HCPQ-Q3, HCPQ-Q5, HCPQ-Q11, HCPQ-Q14, HCPQ-Q16, HCPQ-Q17)
 
“TFLs_TOC_HEART_Example_lay outs/T10 HCPQual” (Comments relevant to objective compiled from free text responses in V2eDC, HCPQ and from HCP focus group discussions)
 | 
“TFLs_TOC_HEART_Example_lay outs/T4 V2eDC-1” (HCP views summed over all participants processed)
 
“TFLs_TOC_HEART_Example_lay outs/T5 V2eDC-2” (HCP views at start of study)
 
“TFLs_TOC_HEART_Example_lay outs/T6 V2eDC-3” (HCP views at end of study)
 
“TFLs_TOC_HEART_Example_lay outs/T8 HCPQ”
 |
| | PCC feedback via focus group | “TFLs_TOC_HEART_Example_lay outs/T11 PCCQual” (Comments relevant to objective compiled from PCC focus group discussions) | N/A |

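### Secondary objective 1: clinicians attribute treatment changes after seeing the IRT, and no visible SAP table checks those attributions against the two scores

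*Protocol*

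**What the plan says.** Protocol 3.5 defines secondary endpoint 1 as treatment changes, based on the risk scores, at Visit 2. Protocol section 4 makes the study single-arm, with both scores given to everyone and no blinding.

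Of the QRISK2 information, the Visit 1 data list (Protocol 7.1.7.1) holds only the score, "QRISK®2 score (when available". No intended management is recorded there. The same section fixes the order of events: "When the QRISK®2 score is available, this will be added to The HEART Application as it is required to calculate the CVD IRT".

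Both attribution items are collected at Visit 2 (Protocol 7.1.8). One is "whether QRISK®2 score required change in treatment (e.g., statin, life style, both or none influenced the change". The other applies if the participant's "CVD IRT score was higher than their QRISK score, whether the CVD IRT score influenced (or informed on) a change in treatment". Protocol 7.2.3 times the HCP form: "When the CVD IRT report has been received and discussion with the participant has taken place, the HCP will be required to complete" it. Protocol 7.1.8 also recommends following NICE guidance where either score exceeds 10%.

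Protocol 10.3.1 promises to assess the "impact of the CVD IRT on clinical decision making where the addition of genetic information shows an increase in risk". The SAP 7.5 row for objective 1 draws on V2eDC items, HCPQ items, free text and HCP focus groups, with DT2 as the key layout. Its supporting tables include one described as "HCP views at start of study". The table "T13 Risk classification" is listed under objective 2 only.

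**The concern.** There is no comparator arm, so a statement about the effect of the IRT on decisions needs some view of what QRISK2 alone would have led to. In this plan the HCP supplies that view once the IRT is known. The supporting table for the start of the study is no exception. It is a V2eDC table, so it covers the earliest Visit 2 forms, and those also follow the report.

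The IRT item is broad. It asks whether a higher IRT influenced or informed a change, and any excess over QRISK2 is enough to trigger it. With QRISK2 at 14% and IRT at 15%, NICE guidance already applied on QRISK2, yet the same statin can be entered under both items. If the report gives a single percentage of IRT-influenced changes, readers may take it as treatment that the genetic component added. Some of it may be treatment that QRISK2 would have prompted anyway.

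**Working it through.** The plan states no figure for objective 1, so there is none to reproduce. The check has two parts: which participants can enter the IRT-influenced count, and how large the informative group might be.

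**1. Score groups against the IRT item.** Inputs are the trigger for the item (IRT above QRISK2) and the common 10% threshold, both from Protocol 7.1.8.

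| QRISK2 | IRT | Is the IRT item asked? | Did NICE guidance apply on QRISK2 alone? |
|---|---|---|---|
| 10% or less | 10% or less | Only if IRT is higher | No, and not on IRT either |
| 10% or less | above 10% | Always, since IRT must be higher | No; the IRT alone crosses |
| above 10% | above 10% | Only if IRT is higher | Yes |
| above 10% | 10% or less | Never | Yes |

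Three of the four groups can contribute to an IRT-influenced count. In only one of them does the IRT alone cross the threshold. In that group the item is asked of everyone, so the most informative group is fully covered by the existing form. In the last group the item is never asked, so it cannot capture a decision to hold back because the IRT is lower.

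**2. Are the data for the check available?** QRISK2 must be entered before the IRT can be calculated, so it cannot be altered by knowledge of the IRT. The HEART Application generates a participant ID that is used in all study documentation (Protocol 7.1.7.1), so scores and Visit 2 entries can be linked. The attribution items are separate, so a yes to both can be told apart from a yes to the IRT item alone.

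**3. Does a visible analysis use them?** The objective 1 row in SAP 7.5 lists no table by score. T13 sits under objective 2. The participant subgroups in SAP 7.6.1 are sex, age, ethnicity and education, not risk score. The DT2 layout and the V2eDC wording are in annexes not seen.

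**4. Rough size of the informative group.** The documents do not give the proportion of participants with QRISK2 at 10% or less; assume 50% to 100%. Protocol 1.2 cites 6.4% of younger middle-aged people missed by QRISK2 as reaching 10% or more on the IRT. Applying that rate to ages 45-64 is a further assumption.

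- 1000 × 100% × 0.064 = 64
- 1000 × 50% × 0.064 = 32
- 800 (assumed 80% completion) × 50% × 0.064 = 25.6, about 26

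If half of the group had an IRT-influenced change (assumed, the least precise case), the Wilson 95% intervals, ignoring clustering by site, are:

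- 32/64: 38.1% to 61.9%
- 16/32: 33.6% to 66.4%
- 13/26: 32.1% to 67.9%

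That is imprecise, but usable for a descriptive objective.

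**The case against.** The strongest reply is that the plan promises no counterfactual estimate. The aim is to describe, objective 1 is to explore and assess, and SAP 7.5 meets each objective by holistic assessment. To say that the IRT informed a change does not claim that the change would otherwise not have happened, and a higher score can reasonably inform a decision without crossing 10%. The two items are asked separately, so causes are mixed only if the report pools them, and the visible text does not say that it will. The unseen DT2 layout may already stratify by score.

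Much of this stands, and it makes the point an improvement to a descriptive analysis. It does not remove the point. A percentage reported with a 95% interval still needs a clear meaning, and no visible row supplies one that is specific to the IRT. If DT2 already has the cross-table, the sponsor need only say so.

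A reader might go further and infer that QRISK2-driven and IRT-driven changes can be separated only in hindsight, with nothing to check the HCP against. The documents do not support that. The score entered before the IRT and the shared threshold give a participant-level check. A threshold rule is not the HCP's own plan, but it does not depend on the HCP's recollection.

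A reader might also infer that a QRISK2-only plan must be recorded before the report is released. That is a matter of judgement. It adds a non-routine step to a study of routine workflow and may anchor the later decision. Patient preference and the 5-12 weeks before results would also show up as plan changes.

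**Conclusion.** The point holds as a gap in the analysis plan. HCP attribution for objective 1 is retrospective, and the trigger for the IRT item lets the count include patients already above 10% on QRISK2. The data that would separate them are collected, but the visible objective 1 row leaves them unused.

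No size of bias can be derived from the documents, and none is claimed. On the assumptions shown, the group where the IRT alone crosses 10% would number roughly 26 to 64. The conclusion rests on the Visit 2 list in Protocol 7.1.8 and the SAP 7.5 row. The annexes could show that part of the gap is already closed, but no form completed after the report can make the attribution prospective.

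One further step is tempting and should not be taken: crediting treatment started before report release to QRISK2. Protocol 7.1.8 allows early action on QRISK2 at the physician's discretion, but its Visit 2 list has no treatment date. Existing data would not reliably identify those changes.

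**What to change.** In SAP 7.5, objective 1, add a key table with number, percentage and 95% CI of Visit 2 treatment changes:

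- by QRISK2 (10% or less, above 10%) and IRT (10% or less, above 10%);
- within each group, by the two attribution items: QRISK2 required a change (yes/no) and IRT influenced a change (yes/no), marking where the IRT item was not asked.

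Name the group with QRISK2 at 10% or less and IRT above 10% as the main evidence of IRT impact. Report entries with yes to both items separately. Label the attributions throughout as retrospective HCP opinion.

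The cost is one extra table from data already collected. The drawback is a smaller denominator, with wider intervals and probably a less favourable headline percentage than a pooled count.

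A dated QRISK2-only plan entered before report release is optional. At an assumed 1-2 minutes per entry and 50-100 participants per site, it takes 50 × 1 = 50 to 100 × 2 = 200 minutes per site. The workflow and anchoring drawbacks above still apply. Attribute early changes to QRISK2 only if a treatment date is also collected.
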